Underlay and overlay technique of myringoplasty have been used for several years, and both have their advantages and disadvantages. When the underlay technique is used to repair the subtotal tympanic membrane perforation, the anterior portion of graft may fall away resulting in reperforation, and obliteration of the anterior part of middle ear cavity. The overlay technique has a higher success rate for the reconstruction of the subtotal tympanic membrane perforation, but lateralization of the graft may occur (*Kartush et al., 2002*).

These problems have been managed by a variety of surgical techniques such as the use of William's microclip, sandwich graft tympanoplasty, loop overlay tympanoplasty, and over-underlay tympanoplasty (*Lee et al., 2010*).

Over-underlay tympanoplasty is a safe, simple and easy procedure with low rate of graft failure and better hearing improvement (*Prakas et al., 2014*).

Yet, a still better method is needed to repair anterior tympanic membrane perforations (*Kartush et al., 2002*)

As a solution, this study aims to apply a modification of several previously reported techniques by using endoscopic double anterior and posterior tympanomeatal flaps and compare it with single posterior tympanomeatal flap as regard success rate in the challenging total and subtotal perforations.

Hypothesis:

To test the role of graft placement under the anterior flap in success rate of tympanoplasty.

Aim of work

The aim of this work is to compare outcome between endoscopic single and double flap technique in repairing total and subtotal tympanic membrane perforations.

Outcomes:

Primary outcome:the difference in graft taking rate between the two techniques.

Secondary outcomes:1-Post operative hearing results.

2-Benefits of endoscope in tympanoplasty.

Patients and methods:

A prospective randomized controlled clinical study will be conducted in Otorhinolaryngology Department, Mansoura University Main Hospital, on 40 patients with total and subtotal tympanic membrane perforations attending in the department.

Period of study:

1 year from July 2017 to July 2018.

Method of randomization:

Randomized according to random table design.

Patients will be divided randomly into 2 groups A and B:

Group A:will undergo single posterior tympanomeatal flap.

Group B:will undergo double anterior and posterior tympanomeatal flaps.

Inclusion criteria:

-Age group (20-50)

-Chronic otitis media with total or subtotal tympanic membrane perforation.

-No active inflammation of middle ear and no epithelial invagination or cholesteatoma mass.

Exclusion criteria

-Recurrent perforation after previous myringoplasty.

-Active inflammation of middle ear.

-Narrow external auditory canal.

-Ossicular disruption or fixation.

-Immunocompromised patients including uncontrolled diabetics, chronic liver and kidney diseases.

Preparation:

-All patients are subjected for pre-operative pure-tone audiograms with planned post-operative audiograms for follow up.

-Written consent will be obtained from patients.

Surgical technique:

-Surgery will be applied under local or general anesthesia via endoscopic trans-canal approach.

-Group A(Single tympanomeatal flap group):-

- The procedure begins with a transcanal endoscopic examination of the TM.
- A temporalis fascia graft is harvested in standard fashion, pressed, and then dried.
- A rim of tissue is removed from the edges of the perforation to ensure complete de-epithelialization of the medial surface of the TM remnant.
- A posterior canal wall incision is made 6-8 mm from annulus from 6 to 12 O'clock, then posterior tympanomeatal flap is elevated with the posterior tympanic annulus to enter middle ear space.
- Tympanic membrane is dissected from handle of malleus.
- The status of the middle ear and ossicular chain are examined.
- The previously harvested fascia graft is trimmed to appropriate size for full coverage of the perforation and placed over handle of malleus, below remnant of tympanic membrane.
- The graft is draped properly to provide complete coverage of the TM perforation.
- The tympanomeatal flap is then laid back down in native position.

-Group B(Double tympanomeatal flaps group):-

- Posterior tympanomeatal flap is elevated like group A.
- Then, the anterior tympanomeatal flap is initiated.
- A horizontal incision is made just lateral to the anterior portion of the annulus .
- The canal skin and anterior annular ring are carefully elevated medially with a Rosen Needle.
- The middle ear is entered medial to the annulus using a 1mm right-angle hook to penetrate the middle ear mucosa until the tip of the instrument is visible through TM perforation
- Care is taken to preserve the integrity of the annular ring when making this anterior canal skin tunnel.
- The previously harvested fascia graft is trimmed to appropriate size for full coverage of the perforation and tailored to have anterior tip that will be later pulled from the middle ear through the anterior tympanomeatal flap.
- The posterior tympanomeatal flap is then moved anteriorly.
- The trimmed fascia graft is then placed into the middle ear through the posterior flap.
- The posterior tympanomeatal flap is placed back down into native position, and the fascia graft is draped properly to cover TM perforation with the anterior tip is directly in line with the anterior canal skin tunnel.
- The anterior tip is picked up with the right-angle hook and pulled through the tunnel underneath the tympanic annulus, and out through the canal skin incision and left as a tag which is laid up against the normal anterior canal skin.

In both groups:

- The middle ear is then packed with dry gel foam followed by gel foam soaked with antibiotic solution and antibiotic soaked ribbon gauze.
- A standard ear pressure dressing is applied for the first 24h and then removed.
- The outer canal packing (ribbon gauze) is removed in 1 week at the first post-operative visit
- Antibiotic drops are initiated twice a day for a week until the second post-operative visit.
- Endoscopic follow up evaluation will be carried out after 3 weeks & follow up PTA&Tympanogram will be done after 3 month.
- The 2 groups will be compared as regard middle ear pressure, hearing assessment& success rate.

Data collection and statistical analysis:

Patients' data including preoperative assessment, operative details and postoperative follow up will be recorded, tabulated, analyzed and discussed.

Sample size: Based on a pilot trial, a convenient sample size was calculated to achieve 80% power to compare outcome between endoscopic single and double flap technique in repairing total and subtotal tympanic membrane perforations with an alpha level of 0.05. Twenty patients per arm will be included in the study.

Data distribution will be analyzed by computer by SPSS program.

Statistical analysis will be performed by using the suitable statistical methods and tests of significance and differences will be considered significant at $P \leq 0.05$.

References:

1. APPLEBAUM, E. L. & DEUTSCH, E. C. 1986. An endoscopic method of tympanic membrane fluorescein angiography. *Ann Otol Rhinol Laryngol*, 95, 439-43.

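### Does the plan's silence on concealment, timing of eligibility and analysis set call for a change?

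*Combined protocol and SAP*

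**What the plan says.** Under Method of randomization the protocol states "Randomized according to random table design" and then "Patients will be divided randomly into 2 groups A and B". This describes how the sequence is made and nothing else.

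The Exclusion criteria include "Ossicular disruption or fixation" and "Narrow external auditory canal". Under Preparation, every patient has a pre-operative pure-tone audiogram. Under Surgical technique, the Group A steps include a look at the middle ear and ossicular chain once the posterior flap is up. Group B raises the same posterior flap first and only then departs from Group A: "A horizontal incision is made just lateral to the anterior portion of the annulus".

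On analysis, the text for both groups says "The 2 groups will be compared as regard middle ear pressure, hearing assessment& success rate". The Sample size paragraph says "Twenty patients per arm will be included in the study". The data section says that patients' "data including preoperative assessment, operative details and postoperative follow up will be recorded, tabulated, analyzed and discussed". No analysis set is named.

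**The concern.** The surgeon cannot be blinded to the technique. Hiding the next assignment until a patient is enrolled is therefore the main guard against steering patients to an arm. Two exclusions leave room for judgement. Canal narrowness has no threshold, and only Group B has an anterior canal incision, so a borderline canal might be judged differently by someone who knew the next assignment. That is an inference; the protocol does not say it. The other is the ossicular exclusion. The only ossicular inspection named is an operative step. Neither it nor the audiogram is linked to eligibility, and the plan does not say how a patient found ineligible on the table is handled.

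If such patients were dropped from one arm more than the other, the graft take rates would rest on selected denominators. With 20 per arm, each patient is 1/20 = 5 percentage points of the primary outcome.

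**Working it through.** **The plan's own figure.** Two arms of 20 give the stated total of 40. The power claim behind the 20 cannot be reproduced, because no take rates are given. That is a separate matter and is not used here.

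**What the text permits.** Inclusion, exclusion, consent and audiogram all precede the operative steps on the page. Because both arms begin with the same posterior flap, assignment after the inspection is also compatible with the text. Under that order an ossicular exclusion found on the table would arise before assignment. No sentence removes or switches a patient after assignment.

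**Assumed inputs.** True take is equal in both arms at 0.70, 0.80 or 0.90, so average failure f is 0.30, 0.20 or 0.10. Two of 20 ears fail at 2f. The other 18 then fail at (20f − 4f)/18 = 0.889f, which keeps the average at f. The test is two-sided Fisher at p ≤ 0.05.

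**Bias.** Without the two higher-risk ears, take rises by f − 0.889f = 0.111f, which is 3.3, 2.2 and 1.1 points. For scale, the standard error of the difference, √(2 × take × f / 20), is √0.021 = 14.5, √0.016 = 12.6 and √0.009 = 9.5 points.

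**False-positive rate.** For each scenario, sum P(a)P(b) over all pairs of success counts whose Fisher p is at most 0.05. Each count is the sum of its ordinary-ear and higher-risk-ear binomials. For random loss of two ears, weight the cases of 0, 1 or 2 higher-risk ears lost by 153/190, 36/190 and 1/190.

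| Scenario | Take 0.70 | Take 0.80 | Take 0.90 |
|---|---|---|---|
| 20 v 20, nothing lost, two-sided | 0.0214 | 0.0208 | 0.0113 |
| 20 v 18, two higher-risk ears dropped, two-sided | 0.0364 | 0.0335 | 0.0180 |
| 20 v 18, two ears lost at random, two-sided | 0.0296 | 0.0305 | 0.0202 |
| 20 v 20, ordinary ears enrolled instead, two-sided | 0.0264 | 0.0234 | 0.0109 |
| Wrongly favouring the affected arm: nothing lost | 0.011 | 0.010 | 0.006 |
| Same: selective drop | 0.028 | 0.023 | 0.009 |
| Same: random loss | 0.016 | 0.015 | 0.007 |

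The selective-drop row must be read against random loss, because Fisher's test is coarse at these sizes and moves with the denominator alone. At take 0.70, random loss accounts for (0.0296 − 0.0214)/(0.0364 − 0.0214) = 55% of the rise. At 0.80 it accounts for (0.0305 − 0.0208)/(0.0335 − 0.0208) = 76%. At 0.90 selective dropping gives a lower two-sided rate than random loss.

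Unconcealed assignment corresponds to the fourth row, where another patient is enrolled in place of the avoided one. The two-sided rate changes by at most 0.0264 − 0.0214 = 0.005, and at 0.90 it falls slightly.

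**Extreme case.** Suppose both dropped ears are certain failures and both come from the better arm. Then 14/20 v 18/20 (p = 0.235) becomes 14/20 v 18/18 (p = 0.021), and 15/20 v 18/20 (p = 0.41) becomes p = 0.048. With 16/20 as comparator, p goes only from 0.66 to 0.107. Nothing in the plan calls for such drops.

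**The case for a change.** The omissions are real, and the ossicular point is specific to this trial: an excluded condition may first be seen on the table, possibly after assignment. In a trial this small, one or two patients can move a p-value across 0.05, as the extreme case shows. The directional error also survives a fair baseline: 0.028 against 0.016 at take 0.70 is more than discreteness. Writing down the order of events and the analysis set would cost a few lines.

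What stands is that the text is silent and that selective loss would favour one arm somewhat. What does not stand is the step from silence to a faulty result. The harm needs three things the documents do not show: that assignments are known in advance, that patients are dropped or avoided by arm, and that canal width or ossicular status affects graft take. Nor would an as-assigned rule settle everything, because it does not say how to count a graft that was never examined.

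**Conclusion.** No change is needed. This is a gap in detail that a competent team fills in the usual way: eligibility and consent first, assignment next, and all patients compared in the groups to which they were randomised. The wording on two randomised groups of twenty, with operative details and follow-up recorded for patients, supports that reading and contradicts none of it.

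On the assumed inputs, even selective absence of two higher-risk ears from one arm shifts its take rate by about 1 to 3 points. That is less than one patient in 20 and well inside sampling error of about 10 to 15 points. All two-sided rates stay below 0.05. The conclusion rests on the assumed take rates, on two higher-risk ears per 20 at twice the failure risk, and on the absence of any rule that removes patients after assignment. It would not hold if ears were in fact dropped after failing, and from one arm only.

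### Total and subtotal perforations are enrolled together with no stratification, blocking or adjustment by type described; stratifying would be a cheap gain in precision and credibility

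*Combined protocol and SAP*

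**What the plan says.** Under Inclusion criteria the plan admits "Chronic otitis media with total or subtotal tympanic membrane perforation". It does not define where subtotal ends and total begins, and it gives no expected mix of the two.

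The description of allocation, under Method of randomization, is "Randomized according to random table design", followed by the statement that patients are split at random into groups A and B. The Sample size paragraph adds "Twenty patients per arm will be included in the study". No stratification, blocking or minimisation is mentioned.

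The primary outcome is "the difference in graft taking rate between the two techniques". The section on data collection and statistical analysis names no test and no covariate; it promises only suitable methods and a significance threshold of 0.05. It does say that preoperative assessment will be recorded.

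In Group A the graft is "placed over handle of malleus, below remnant of tympanic membrane". In Group B its anterior tip is drawn through a tunnel under the annulus. The stated hypothesis concerns the role of placing the graft under the anterior flap.

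**The concern.** Perforation type is an entry criterion, so it can be known before assignment. It is also a natural candidate prognostic factor. The trial tests a way of securing the anterior edge of the graft, and the Group A graft is positioned against the drum remnant, so the amount of remnant bears on the mechanism under study. Yet type is controlled neither in the allocation nor in the analysis.

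With 20 per arm, a visible chance imbalance in type is fairly likely. If one occurs, the plan offers no prespecified answer to a reader who asks how much of the difference in take is due to it, and any adjustment would be a post hoc choice. A single graft can matter near the threshold: by Fisher's exact test, 13/20 against 19/20 gives P = 0.044, and 14/20 against 19/20 gives P = 0.091.

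**Working it through.** **The plan's own figure.** The plan says "a convenient sample size was calculated to achieve 80% power" "with an alpha level of 0.05", resting on a pilot ("Based on a pilot trial") whose take rates are not reported. So 20 per arm cannot be reproduced; it can only be placed on a range. The pooled two-proportion formula, two-sided, without continuity correction, is

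n = [1.96·√(2·p̄·(1−p̄)) + 0.8416·√(p₁(1−p₁)+p₂(1−p₂))]² / (p₁−p₂)².

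For 50% against 90%: [1.96·√0.42 + 0.8416·√0.34]² / 0.16 = 1.761² / 0.16 = 19.4, so 20 per arm. Across better-arm take rates from 80% to nearly 100%, 20 per arm has 80% power only for differences of about 31–42 points, or roughly 6 to 8 grafts of 20.

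**Chance of imbalance.** Inputs: 40 ears and 20 per arm (Sample size); K total perforations (assumed). With arms fixed at 20/20, the number of total perforations in one arm, X, is hypergeometric (40, K, 20), and the arms differ by |2X − K| patients. Four patients is 20 points; six is 30 points.

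| K | at least 4 patients | at least 6 patients |
|---|---|---|
| 8 | 23.5% | 4.4% |
| 10 | 27.3% | 6.5% |
| 12 | 30.1% | 8.2% |
| 16 | 33.3% | 10.5% |
| 20 | 34.3% | 11.3% |

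For K = 10, for example, a difference of 4 or more needs X ≤ 3 or X ≥ 7: 2 × (0.10425 + 0.02824 + 0.00396 + 0.00022) = 0.273. When K is odd the difference must be odd, so at least 4 means at least 5; the chance is then 16–20% for K from 11 to 19.

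If each assignment were instead an independent coin toss, simulation puts the chance of a 20-point difference in share at 14–27% for K from 8 to 20.

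**Shift in the take-rate difference.** Let d be the difference between arms in the share of total perforations, and g_A and g_B the gaps in take between subtotal and total ears in each arm (assumed; the documents give none). The shift caused by imbalance is d × (g_A + g_B)/2.

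- Same gap in both arms: 0.20 × 0.20 = 4 points, up to 0.30 × 0.30 = 9 points, that is 0.8 to 1.8 grafts of 20.
- Gap in one arm only: 0.20 × 0.10 = 2 points, up to 0.30 × 0.15 = 4.5 points.

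For comparison, the sampling standard error √(2p(1−p)/20) is 12.6 points at 80% take and 9.5 points at 90%.

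**Effect on precision.** Take K = 20, subtotal take 90% (assumed), no treatment effect. Under stratified allocation the variance of the difference is 2 × [10·p_T(1−p_T) + 10·0.9·0.1] / 400, where p_T is take in total ears. Without stratification, add g² × 0.02564, the last factor being the variance of the difference in share.

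- g = 0.20: 0.0150 against 0.0150 + 0.0010 = 0.0160. SD 0.122 against 0.127; variance lower by about 6%.
- g = 0.30: 0.0165 against 0.0165 + 0.0023 = 0.0188. SD 0.128 against 0.137; variance lower by about 12%.

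**Error rates.** These come from simulation with an unstratified Fisher test (300,000 runs per case). Under no treatment effect, type I error is 2.2–2.3% with unstratified allocation and 1.6–1.8% with stratified allocation. With a 30-point effect (single-flap take of 69% in subtotal ears) and 20 total ears, power is 48% against 48% for a 20-point gap, and 44% against 43% for a 30-point gap.

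**The case against.** A reader might infer three stronger claims, and the documents support none of them.

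**That allocation is unrestricted.** The plan is silent on this; it does not say the table is single, simple or unblocked. Fixing the arms at twenty is compatible with using a table to permute 40 slots. Under independent draws an exact 20/20 split would arise only 12.5% of the time, but that shows the description is incomplete, not that coin-toss allocation is planned. Nothing suggests that an arm is closed once it is full.

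**That total perforations are the harder ears.** The introduction calls both types challenging and gives no separate take rates. Its remark about the anterior part of the graft falling away concerns underlay repair of subtotal perforations. The Group A graft, laid over the malleus handle, resembles the over-underlay method, which the introduction credits with few failures. The prognostic gap is therefore an assumption, and so is any greater effect in Group A.

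**That the comparison would be biased or impossible to disentangle.** Chance imbalance under randomisation is already allowed for by the test, and the shift is smaller than the sampling error. Preoperative assessment is recorded, so take could be tabulated or adjusted by type afterwards, though not in a prespecified way.

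It can also be said that one or two grafts are few beside the 6 to 8 that 20 per arm can detect, and that stratification does next to nothing for power. Both points stand, and they limit the weight of this one. They do not remove it: a factor known at entry and tied to the mechanism under test is left uncontrolled, and controlling it is nearly free.

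**Conclusion.** The point holds as a moderate matter of precision and credibility. Type is handled neither in the described allocation nor in the planned analysis. With arms fixed at 20/20, a 20-point imbalance in type would arise in about one randomisation in four to one in three for even counts of 10 to 20 total perforations, and less often for odd counts or coin-toss allocation. The 9-point end of the shift needs a 30-point gap in both arms together with a 30-point imbalance, which itself has a chance of at most about 11%.

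Stratification would lower the variance of the difference by some 6–12% in the cases shown, and would cost almost nothing if no gap exists. All of this rests on an assumed mix and an assumed gap in take. Nothing here invalidates the trial, and the unreported pilot rates behind the sample size are a larger gap in the plan.

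**What to change.** In Method of randomization, state how the list is generated. Define total and subtotal perforation, and require each ear to be classified before its assignment is opened. Replace the random table with two permuted-block lists with varying block sizes, one per perforation type. In the analysis section, prespecify a comparison of graft take stratified by type (Mantel-Haenszel or an exact stratified test), and report type and take by arm.

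If enrolment is complete, make only the analysis change and add the table.

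The cost is a few protocol sentences, a stratum definition and a second list, with no extra patients. The timing needs care: Preparation mentions only audiograms and consent, and the endoscopic examination is listed as the first operative step, so the plan must say when the classification is recorded relative to assignment. Incomplete last blocks may leave the arms one or two patients away from 20/20.

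### Does the unexplained 80% power figure for 20 patients per arm call for a change to the plan?

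*Combined protocol and SAP*

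**What the plan says.** The Outcomes section names one primary outcome: "Primary outcome:the difference in graft taking rate between the two techniques". Hearing and the benefits of the endoscope are secondary.

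Under Data collection and statistical analysis, the sample-size paragraph refers to a pilot trial and states that "a convenient sample size was calculated to achieve 80% power to compare outcome between endoscopic single and double flap technique" at an alpha of 0.05. It ends: "Twenty patients per arm will be included in the study". It gives no pilot counts, take rates, target difference, test or sidedness.

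The analysis text that follows is equally general: "Statistical analysis will be performed by using the suitable statistical methods and tests of significance", with significance at P ≤ 0.05. The list of steps common to both groups closes with "The 2 groups will be compared as regard middle ear pressure, hearing assessment& success rate".

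**The concern.** The power sentence speaks only of outcome, and the plan compares the groups on three measures. Taken literally, the 80% might belong to any of them. If it was meant for graft take, a binary outcome with 20 patients per arm detects only large differences. The introduction adds some unease: it says "Over-underlay tympanoplasty is a safe, simple and easy procedure with low rate of graft failure and better hearing improvement", and the Group A graft is "placed over handle of malleus, below remnant of tympanic membrane", a similar position. If single-flap take is already high, there is little room for a gain of 26 to 39 points.

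Two things would be at stake. A non-significant result printed beside an unqualified 80% could be taken as good evidence that the techniques do equally well, although the confidence interval would be wide. And with few failures, the choice between an uncorrected chi-square and Fisher's exact test can decide which side of 0.05 the result falls, while the plan names neither.

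**Working it through.** **Inputs from the documents:** 20 per arm, alpha 0.05, significance at P ≤ 0.05, target power 80%, primary outcome graft take.

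**Inputs not in the documents (assumed):** a two-sided test, double-flap take rates of 100%, 95% and 90%, and no dropout.

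**The plan's own figure.** Twenty per arm cannot be re-derived, because no rates or difference are given. The calculation can only be run backwards, asking which differences 20 per arm detects with 80% power.

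**Method.** With A ~ Bin(20, pA) and B ~ Bin(20, pB), power = Σ P(A = a) × P(B = b), summed over the tables (a, b), out of 21 × 21, that give P ≤ 0.05.

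**A case that can be checked by hand.** If double flap takes 100%, then b = 20 always.
- 20/20 vs 16/20, Pearson: the pooled rate is 36/40 = 0.90, so χ² = 0.20² / (0.90 × 0.10 × 2/20) = 0.04/0.009 = 4.44 and P = 0.035.
- 20/20 vs 16/20, Fisher: P = 2 × C(20,4)/C(40,4) = 2 × 4845/91390 = 0.106.
- 20/20 vs 17/20, Pearson: P = 0.072. 20/20 vs 15/20, Fisher: P = 0.047.

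So Pearson rejects when a ≤ 16 and Fisher when a ≤ 15. Power is P(A ≤ 16) or P(A ≤ 15). At pA = 0.65 these are 0.956 and 0.882. At pA = 0.80 they are 0.589 and 0.370.

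**Highest single-flap take rate that still gives 80% power, two-sided:**

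| Double flap (assumed) | Pearson: rate (difference) | Fisher: rate (difference) |
|---|---|---|
| 100% | 74.1% (25.9 points) | 68.7% (31.3 points) |
| 95% | 61.1% (33.9 points) | 56.0% (39.0 points) |
| 90% | 52.1% (37.9 points) | 47.2% (42.8 points) |

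**Power at selected assumed rates, two-sided:**

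| Double vs single | Pearson | Fisher |
|---|---|---|
| 100% vs 65% | 96% | 88% |
| 95% vs 65% | 72% | 59% |
| 100% vs 80% | 59% | 37% |
| 95% vs 80% | 29% | 17% |

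The ranges are not exhaustive. A Yates-corrected test needs about 37 points at 100% and 40 at 95%. A one-sided uncorrected Pearson test at 100% needs about 20 points (single flap 79.8%).

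**Interval width.** For an observed 19/20 vs 17/20 the difference is 10 points, with a Newcombe 95% interval of −11 to +31 points.

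**Is the power sentence detached from graft take?** The Aim of work section describes the whole study with the same phrase that the power sentence uses: comparing outcome between the two flap techniques in these perforations. There is one named primary outcome, and both the introduction and the Hypothesis are about success rate. Middle ear pressure is not among the listed outcomes at all. If hearing had been powered, 20 per arm would correspond to 0.91 SD on a two-sided t test, but nothing in the text points that way.

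**Does the introduction contradict a large difference?** It attaches no number to a low failure rate and does not call Group A over-underlay. It goes straight on to say "Yet, a still better method is needed to repair anterior tympanic membrane perforations", and it warns that underlay grafts in subtotal perforations can lose their anterior support. It does not settle the single-flap take rate either way.

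**The case for a change.** The strongest case for a change is that the 80% is the only justification offered for the size of the trial, and no reader can check it. Stating the outcome, pilot counts, test and sidedness would take one paragraph and no extra patients. Naming the test in advance would remove a choice that, at 20/20 vs 16/20, separates P = 0.035 from P = 0.106. The large differences required also make a quiet misreading of a null result possible.

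Much of this stands. The omission is real, the arithmetic is sound, and a fuller paragraph would be better reporting. What does not stand is the step from a missing input to a faulty plan. Every rate behind the 26-to-39-point range is assumed, and the claim holds comfortably in one of the scenarios shown. Nowhere does the plan say that P > 0.05 will be read as equivalence, so that harm depends on a misuse the documents do not propose. On the test, 20/20 vs 16/20 has an expected failure count of 2 per arm, and Fisher's exact test is an ordinary choice for a table that sparse.

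**Conclusion.** No change follows. The sample-size paragraph is incomplete: 20 per arm can be neither confirmed nor refuted from what is written. Under assumed double-flap rates of 100% and 95% and a two-sided 0.05 test, 80% power for graft take needs about 26 to 31 points and 34 to 39 points respectively, the lower end for uncorrected Pearson and the upper for Fisher. Those figures illustrate what the design can detect; they do not contradict any number in the plan. The documents do not show that the trial is underpowered.

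This is a gap that analysts fill sensibly. The primary outcome is clear, the natural reading ties the power to it, and a suitable test of two proportions in a small table is standard work. Nothing in the plan would produce a wrong result if followed. The conclusion rests on reading outcome in the power sentence as the single primary outcome, and on the pilot rates being unknown rather than unfavourable. Anyone interpreting a non-significant result should look at the interval for the difference, not at the 80%.
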